## 8.6.3. Vital Signs Parameters

All vital signs parameters, will be listed, as applicable; any value outside the clinical reference range will be flagged.

Summary tables by treatment and timepoint will be provided by treatment group for all vital signs parameters as applicable.

# 8.6.4. 12-lead Electrocardiogram Parameters

All 12-lead ECG parameters will be listed; any value outside the clinical reference range will be flagged.

Summary tables by treatment and timepoint will be provided for all 12-lead ECG parameters.

#### 8.6.5. Other Assessments

Medical history will not be listed.

All other safety and tolerability assessments not detailed in the above sections will be listed only.

## 8.6.6. Safety and Tolerability Statistical Methodology

No inferential statistical analyses are planned.

#### 9. INTERIM ANALYSES

No interim analyses are planned.

#### 10. SIGNIFICANT CHANGES FROM THE PROTOCOL-SPECIFIED ANALYSES

There were no significant changes from the protocol-specified analyses.

Final Version 1.0, 15Oct2021

Page 20 of 22

SAP CONFIDENTIAL Covance Study: 8471128 Protocol Reference: 20210093

# 12. APPENDICES

# **Appendix 1: Document History**

Status and Version	Date of Change	Summary/Reason for Changes
Final Version 1.0	NA	NA; the first version.

NA = not applicable

## LIST OF ABBREVIATIONS

Abbreviations pertain to the statistical analysis plan (SAP) only (not the tables, figures, and listings [TFLs]).

ADaM Analysis Data Model

AE adverse event

AUC area under the concentration-time curve

AUCinf area under the plasma concentration-time curve from time zero

extrapolated to infinity

AUClast area under the plasma concentration-time curve from time zero to the

last quantifiable concentration

BLQ below the limit of quantification

CDISC Clinical Data Interchange Standards Consortium

CDER Center for Drug Evaluation and Research

CI confidence interval

CTCAE Common Terminology Criteria for Adverse Events

CL/F apparent total clearance

Cmax maximum observed plasma concentration

COVID-19 coronavirus disease 2019
CRU clinical research unit
CSR clinical study report

CTCAE Common Terminology Criteria for Adverse Events

CV coefficient of variation
DMP data management plan
ECG electrocardiogram
EOS end of study

eCRF electronic case report form
GLSM geometric least square means

ICF informed consent form

ICH International Council for/Conference on Harmonisation

 $\lambda_z$  apparent terminal elimination rate constant

 $\lambda_z$  Lower start of exponential fit

 $\lambda_{z}$  N number of data points included in the log-linear regression

 $\lambda_z$  Span Ratio time period over which lambda z was determined as a ratio of apparent

terminal elimination half-life

 $\lambda_z$  Upper end of exponential fit

LLOQ lower limit of quantification

ln natural log

LSM least squares mean

MedDRA Medical Dictionary for Regulatory Activities

NA not applicable PK pharmacokinetic(s)

R^2-adj adjusted coefficient for determination of exponential fit

SAP statistical analysis plan SD standard deviation

SDV source document verification

 $t_{1/2}$  apparent terminal elimination half-life TEAE treatment-emergent adverse event

TFL table, figure, and listing

 $\begin{array}{lll} t_{last} & \text{time of the last quantifiable plasma concentration} \\ t_{max} & \text{time of the maximum observed plasma concentration} \\ V_z/F & \text{apparent volume of distribution during the terminal phase} \end{array}$ 

WHODrug World Health Organization Drug Dictionary

#### 1. INTRODUCTION

This SAP has been developed after review of the clinical study protocol (Final Version 1.0 dated 04 June 2021, Amendment 1 dated 02 September 2021 and Amendment 2 dated 09 September 2021) and electronic case report form (eCRF).

This SAP describes the planned analysis of the pharmacokinetic (PK), safety, and tolerability data from this study. A detailed description of the planned TFLs to be presented in the clinical study report (CSR) is provided in the accompanying TFL shells document.

In general, the analyses are based on information from the protocol, unless they have been modified by agreement with Amgen Inc. A limited amount of information about this study (eg, objectives, study design) is given to help the reader's interpretation.

This SAP must be finalized prior to the lock of the clinical database. Additionally, the SAP and TFL shells should be finalized prior to any programming activities commencing.

This SAP supersedes any statistical considerations identified in the protocol; where considerations are substantially different, they will be so identified. If additional analyses are required to supplement the planned analyses described in this SAP, they may be performed and will be identified accordingly in the CSR. Any substantial deviations from this SAP will be agreed with Amgen Inc. and identified in the CSR.

This SAP is written with consideration of the recommendations outlined in the International Conference on Harmonisation (ICH) E3 guideline *Structure and Content of Clinical Study Reports*, ICH E8 guideline *General Considerations for Clinical Trials*, ICH E9 guideline *Statistical Principles for Clinical Trials*. 1,2,3

The document history is presented in Appendix 1.

#### 2. STUDY OBJECTIVES

The primary objective of the study is:

• to compare the PK of 960 mg sotorasib administered orally as 3 x 320 mg tablets (test 1) under fasted condition to 960 mg sotorasib administered orally as 8 x 120 mg tablets (reference) under fasted condition.

The secondary objectives of the study are:

- in 14 subjects, to evaluate the PK of 960 mg sotorasib administered orally as 3 x 320 mg tablets with a high-fat meal (test 2).
- to assess the safety and tolerability of 960 mg sotorasib administered orally as 3 x 320 mg tablets and 960 mg sotorasib administered orally as 8 x 120 mg tablets.

#### 3. STUDY ENDPOINTS

The primary endpoints of the study are sotorasib PK parameters in Period 1 and Period 2:

Final Version 1.0, 15Oct2021

Page 6 of 22

- maximum observed plasma concentration (Cmax)
- area under the plasma concentration-time curve (AUC) from time zero to the last quantifiable concentration (AUClast)
- area under the plasma concentration-time curve from time zero extrapolated to infinity (AUCinf).

The secondary endpoints of the study are:

- adverse events (AE)
- clinical laboratory tests
- 12-lead electrocardiograms (ECGs)
- vital signs
- sotorasib PK parameters in Period 3: Cmax, AUClast, AUCinf.

#### 4. STUDY DESIGN

[figure not shown]
This will be an open-label, multi-center (United States), crossover, 3-period bioequivalence study to compare the PK of a single oral dose of 960 mg sotorasib administered as 3 x 320 mg tablets (test 1) under fasted condition to a single oral dose of 960 mg sotorasib administered as 8 x 120 mg tablets (reference) under fasted condition and the PK of 960 mg sotorasib administered as 3 x 320 mg oral tablets following a high-fat meal (test 2) to 960 mg sotorasib administered as 3 x 320 mg oral tablets under fasted condition (test 1) in healthy male subjects and healthy female subjects. Approximately 146 subjects will be enrolled to ensure that at least 132 subjects complete the study.

Potential subjects will be screened to assess their eligibility to enter the study within 28 days prior to the first dose administration. Subjects will be admitted into the Clinical Research Unit (CRU) on Day -1 and be confined to the CRU until discharge on Day 6 or Day 9. On Day 1, subjects will be randomized to Group 1 or Group 2. Each subject will receive one administration of 960 mg sotorasib administered orally as 3 x 320 mg tablets (Treatment A: test 1) and one administration of 960 mg sotorasib administered orally as 8 x 120 mg tablets (Treatment B: reference) in either Period 1 or Period 2 according to their assigned group. Each subject will receive both treatments following an overnight fast according to the treatment sequence in Table below. On Day 7, 14 subjects in either Group 1 or Group 2 will proceed to Period 3 and receive one additional administration of 960 mg sotorasib administered orally as 3x 320 mg tablets with a high-fat meal (Treatment C: test 2).

Group	Period 1 (Day 1)	Period 2 (Day 4)	Period 3 (Day 7)	
1	Treatment A	Treatment B	Treatment C	
2	Treatment B	Treatment A	Treatment C	

An overview of the study design is shown in Figure 1.

Figure 1: Study Design

Abbreviations: EOS = End of Study; ET = Early Termination; N = number of subjects

The total duration of study participation for each subject (from Screening through end of study [EOS]) is anticipated to be approximately 5 weeks.

The start of the study is defined as the date the first enrolled subject signs an Informed Consent Form (ICF). The point of enrollment occurs at the time of subject number allocation. The end of the study is defined as the date of the last subject's last assessment (scheduled or unscheduled).

#### 5. SAMPLE SIZE JUSTIFICATION

The study will require at least 132 subjects completing the study to establish equivalence between the 2 groups with 90% power. This test is based on a 2-sided ratio of means test for a 2 x 2 crossover design for continuous data with significance level 5%. The ratio of means between treatment and control groups under the alternative hypothesis is 0.95. This test assumes lower and upper equivalence limits of 0.8 and 1.25, respectively, and root mean squared error of the log ratio equal to 0.472. Assuming approximately 10% drop out rate, approximately 146 subjects (73 subjects per treatment) will be enrolled in this study.

#### 6. STUDY TREATMENTS

The study treatment names, abbreviations, and ordering to be used in the TFLs are presented in Table .

Table 1:Presentation of Study Treatments in TFLs

Final Version 1.0, 15Oct2021

\*Subjects will receive a single dose in each treatment period, on Days 1, 4, and 7.

\*\* Subjects will be discharged on Day 6 or Day 9 according to their treatment assignment.

Treatments	Abbreviation	Order in TFLs
one administration of 960 mg sotorasib administered orally as 3 x 320 mg tablets (Test 1)	Treatment A	1
one administration of 960 mg sotorasib administered orally as 8 x 120 mg tablets (Reference)	Treatment B	2
one administration of 960 mg sotorasib administered orally as 3x 320 mg tablets with a high-fat meal (Test 2)	Treatment C	3

The study treatment sequence names, abbreviations, and ordering to be used in the TFLs are presented in Table 1.

Table 1: Presentation of Study Treatment Sequences in TFLs

For all subjects:

Study Treatment Sequence	Abbreviation	Order in TFLs
one administration of 960 mg sotorasib administered orally as 3 x 320 mg tablets on Period 1 (Day 1) and one administration of 960 mg sotorasib administered orally as 8 x 120 mg tablets on Period 2 (Day 4)	Sequence AB	1
one administration of 960 mg sotorasib administered orally as 8 x 120 mg tablets on Period 1 (Day 1) and one administration of 960 mg sotorasib administered orally as 3 x 320 mg tablets on Period 2 (Day 4)	Sequence BA	2

# For the 14 subjects attending all 3 periods:

Study Treatment Sequence	Abbreviation	Order in TFLs
one administration of 960 mg sotorasib administered orally as 3 x 320 mg tablets on Period 1 (Day 1) and one administration of 960 mg sotorasib administered orally as 8 x 120 mg tablets on Period 2 (Day 4) and one administration of 960 mg sotorasib administered orally as 3x 320 mg tablets with a high-fat meal (Day 7)	Sequence ABC	1
one administration of 960 mg sotorasib administered orally as 8 x 120 mg tablets on Period 1 (Day 1) and one administration of 960 mg sotorasib administered orally as 3 x 320 mg tablets on Period 2 (Day 4) and one administration of 960 mg sotorasib administered orally as 3x 320 mg tablets with a high-fat meal (Day 7)	Sequence BAC	2

Covance Study: 8471128

The summaries will be based on planned treatment sequences and listings will be based on actual treatment sequences (eg, if subject was assigned to receive placebo in Period 1 and active treatment in Period 2 (sequence [A/B]) but was wrongfully dosed with active treatment in Period 1 and discontinued before start of Period 2, they would be summarized under 'A/B' treatment sequence and listed under 'B' treatment sequence).

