The summaries will be based on planned treatment sequences and listings will be based on actual treatment sequences (eg. if subject was assigned to receive placebo in Period 1 and active treatment in Period 2 (sequence [A/B]) but was wrongfully dosed with active treatment in Period 1 and discontinued before start of Period 2, they would be summarized under 'A/B' treatment sequence and listed under 'B' treatment sequence).

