#### 8. STATISTICAL METHODOLOGY

#### 8.1. General

Listings will be provided for all data captured in the database, with the exception of medical history. Listings will include all subjects assigned to the all subjects population and include data up to the point of study completion or discontinuation. Subjects are generally considered to have completed the study if they complete the scheduled end of study visit (rather than early termination visit). Any subject who discontinues the study will be identified accordingly in the listings. Summaries and statistical analyses will include the subjects assigned to the relevant population based on data type.

Data analysis will be performed using the SAS® statistical software package Version 9.4 (or higher if a new version is issued during the study).

Analysis Data Model (ADaM) datasets will be prepared using Clinical Data Interchange Standards Consortium (CDISC) ADaM Version 2.1 (or higher if a new version is issued during the study) and CDISC ADaM Implementation Guide Version 1.1 (or higher if a new version is issued during the study). Pinnacle 21 Enterprise Version 4.2.0 (or higher if a new

version is issued during the study) will be utilized to ensure compliance with CDISC standards.

Caution should be used when interpreting results from the statistical analyses conducted in this study because the sample size is not based on power calculations.

Where reference is made to 'valid' data, this refers to non-missing data which meet the predetermined criteria (eg, are not flagged for exclusion).

Where reference is made to 'all calculations', this includes, but is not limited to, summary statistics, statistical analyses, baseline derivation, changes from baseline, percentage changes from baseline, and any parameter derivations.

All figures will be produced on linear-linear or discrete-linear scales, as applicable, unless specifically stated otherwise.

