#### Mixed Model Analysis

```
proc mixed data = <data in>;
  by parcatln parcatl pkday paramn param;
  class trtan aperiod trtseqp usubjid;
  model lpk = trtan aperiod trtseqp / cl residual ddfm = kr;
  lsmeans trtan / cl pdiff = control('2') alpha = 0.1;
  random intercept / subject = usubjid(trtseqp);
  ods output lsmeans = <data out>;
  ods output diffs = <data out>;
  ods output covparms = <data out>;
run;
```

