## Mixed Model Analysis

```
proc mixed data = <data in>;
  by parcatln parcatl pkday paramn param;
  class trtan usubjid;
  model lpk = trtan / cl residual ddfm = kr;
  lsmeans trtan / cl pdiff = control('2') alpha = 0.1;
  random intercept / subject = usubjid(trtseqp);
  ods output lsmeans = <data out>;
  ods output diffs = <data out>;
  ods output covparms = <data out>;
run;
```

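### SAP section 6 ties summaries to the planned sequence, and nothing says the by-treatment PK and safety tables use the tablet actually taken

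*SAP*

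**What the plan says.** SAP section 6 first lists the treatments (A, B, C), then the sequences (AB, BA, and ABC, BAC for the food-effect subjects). After the sequence tables it gives one rule: "The summaries will be based on planned treatment sequences and listings will be based on actual treatment sequences". The rule appears in both copies of the SAP in the file.

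The example that follows imagines a case "if subject was assigned to receive placebo in Period 1 and active treatment in Period 2". The subject is given the wrong product in Period 1 and leaves before Period 2. The outcome is that "they would be summarized under 'A/B' treatment sequence and listed under 'B' treatment sequence". This trial has no placebo; both products are active sotorasib tablets.

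The output sections are written by treatment: disposition (8.2), demographics (8.3), PK concentrations and parameters (8.5.3), TEAEs (8.6.1), laboratory values (8.6.2), vital signs (8.6.3) and ECGs (8.6.4). None says whether treatment means planned or received.

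The bioequivalence code in 8.5.3 has "model lpk = trtan aperiod trtseqp / cl residual ddfm = kr". The food-effect code has "model lpk = trtan / cl residual ddfm = kr". Neither `trtan` nor `trtseqp` is defined.

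**The concern.** In a crossover, sequence and period together determine which formulation a measurement belongs to. If tables are filled from the planned sequence, a subject given the other tablet contributes that period's data to the wrong column.

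The objectives compare the PK of two tablet presentations and describe the safety of each, so what matters is the tablet swallowed. A TEAE that follows 8 x 120 mg but is counted under 3 x 320 mg makes both columns wrong. The listings, which follow the actual sequence, would then contradict the tables by design. If the model uses treatment received while the PK summary tables use the plan, the same profile could also sit under different tablets in two parts of the study report.

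**Working it through.** **Following the rule through one case.** Take a subject assigned to AB who is given 8 x 120 mg in Period 1 and then withdraws.

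1. Section 6 keeps this subject under AB in summaries and lists the subject under B.
2. Period 1 of AB is Treatment A. A by-treatment table filled from the planned sequence therefore puts the Period 1 data under 3 x 320 mg, although 8 x 120 mg was taken.
3. SAP 8.5.1 derives PK parameters from the actual dose in mg. That dose is 3 x 320 = 960 mg or 8 x 120 = 960 mg, so it cannot show which tablet was taken.
4. SAP section 7 has deviations considered before database lock when populations are assigned. That can remove a subject, but it does not relabel a period. The safety population needs one dose and one postdose safety assessment. The PK population needs one dose and evaluable PK data, and its named exclusions are vomiting and diarrhea. This subject can qualify for both.
5. The SAP bases its datasets on ADaM ("Analysis Data Model (ADaM) datasets will be prepared using Clinical Data Interchange Standards Consortium (CDISC) ADaM Version 2.1"). By that style of naming, `trtan` reads as actual treatment and `trtseqp` as planned sequence. On this reading the models already use the tablet taken.

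**Size if planned labels reached the model.** This is conditional; the code suggests they do not.

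Inputs (SAP section 5): 132 completers, log-scale root mean squared error 0.472, assumed ratio 0.95, limits 0.80 and 1.25. SAP 8.5.3 gives two one-sided tests at 0.05 each.

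The plan's own figure first: SE = 0.472 x sqrt(2/132) = 0.0581 with 130 degrees of freedom. Power at a ratio of 0.95 is 0.902, which reproduces the stated 90%.

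If k of 132 completers have both periods swapped and are analysed as planned, the log ratio is multiplied by (132 - 2k)/132. If each of k completers took the same tablet twice, the factor is (132 - k)/132. The variance is held fixed. At a true ratio of 0.80, on the lower limit:

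| k | Both periods swapped: factor | Expected ratio | False bioequivalence | Same tablet twice: factor | Expected ratio | False bioequivalence |
|---|---|---|---|---|---|---|
| 0 | 1 | 0.8000 | 5.0% | 1 | 0.8000 | 5.0% |
| 1 | 0.985 | 0.8027 | 5.6% | 0.992 | 0.8014 | 5.3% |
| 3 | 0.955 | 0.8082 | 7.1% | 0.977 | 0.8041 | 6.0% |
| 5 | 0.924 | 0.8136 | 8.8% | 0.962 | 0.8068 | 6.7% |
| 7 | 0.894 | 0.8192 | 10.8% | 0.947 | 0.8095 | 7.5% |

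At the assumed ratio of 0.95, one full swap gives exp(0.985 x ln 0.95) = 0.9507, and power moves from 0.902 to 0.904. The values of k are assumed; the documents give no dosing-error rate. The formula does not cover the withdrawn subject above, who is not a completer and has no within-subject difference.

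**The case against.** The strongest reply is that the sentence concerns sequence labels only. It follows the sequence tables, its example assigns a sequence label, and it never says that Period 1 data go under Treatment A. That is fair: carrying the rule to by-treatment tables is an inference. But the SAP describes no summary by sequence. If the rule does not reach the by-treatment tables, it governs no summary described there, and planned versus actual is unspecified for all of them. The table shells, a separate document, might settle this, but the SAP does not. The same correction is needed on either reading.

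A reader might also infer that the rule biases the trial toward concluding bioequivalence. The documents do not support that. The decision rests only on the 90% confidence interval from the mixed model (SAP 8.5.3), and nothing puts planned treatment into that model. Nor is pairing `trtan` with `trtseqp` in the code a defect: treatment received with planned sequence is a sensible specification.

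Finally, mix-ups are unlikely and would be seen. The study is open-label, three tablets look different from eight, dosing is supervised, and product is inventoried before and after each dose (protocol 5.7 and 5.8). The questionnaire in protocol Appendix 8 records the regimen just taken, and listings show the actual sequence. This stands, and it limits how much the point matters. It does not correct the wording of the rule.

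**Conclusion.** The point holds as a low-priority correction to a stated rule. Followed literally, SAP section 6 would place a mis-dosed period's PK values and TEAEs under the tablet not taken, and no other provision reassigns them. The exposure is to the descriptive PK and safety tables and to their agreement with the models and listings. The bioequivalence and food-effect estimates are probably unaffected, provided `trtan` means actual treatment, which the SAP leaves undefined.

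The effect is zero if every dose is given as assigned. The shrinkage above applies only if planned labels enter the model and completers are mis-dosed. Even then, one full swap raises the false-bioequivalence risk only from 5.0% to 5.6%.

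**What to change.** Replace the sentence and its placebo example in SAP section 6 with: 'PK and safety summaries and the PK statistical analyses use the treatment actually received in each period; planned sequence is used for disposition and for the sequence effect in the mixed model.' Align SAP 8.2, which now gives the disposition table by treatment. In 8.5.3, define `trtan` as actual treatment and `trtseqp` as planned sequence.

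Do not change the model's sequence term to the sequence actually received. The withdrawn subject above would then form a sequence level B with one subject and one observation, which the fixed effect absorbs, so that record would add nothing to the treatment estimate. A subject given the same tablet twice would likewise create a BB or AA level.

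The cost is a few lines of SAP text. No new data are needed: protocol Table 2 already has the quantity, date and lot number of product given recorded on each subject's Case Report Form.

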# 7. DEFINITIONS OF POPULATIONS

Any protocol deviations, including those due to coronavirus disease 2019 (COVID-19) and related restrictions (see Section 8.1.1), will be considered prior to database lock for their importance and taken into consideration when assigning subjects to populations.

